Rationale: The Small Airways are a major site of obstruction in many respiratory diseases, including COPD. More insight into a diagnosis of Small Airways Dysfunction (SAD) in patients with COPD is clinically valuable as it might enable tailored pharmacotherapy. Currently, methods to diagnose SAD in COPD are not standardized and are not available in routine clinical practice. The Small Airways Dysfunction Tool (SADT) was developed to identify patients with asthma and SAD. Initially, the SADT included a comprehensive 63-item questionnaire. The number of items has been reduced to a SADT-asthma (SADT-a) questionnaire and key patient and disease characteristics for it to be feasible and implementable in clinical practice. Although there are many similarities between asthma and COPD, there might be differences in clinical characteristics and responses to small airways dysfunction between the two diseases.

The current study aims to adapt the original 63-item SADT questionnaire for dedicated use in COPD by reducing the number of items, and identifying COPD-SAD-specific items, to enhance its efficiency in identifying SAD when combined with key patient and disease characteristics in individuals with COPD (SADT-c). In addition, a comparison of diagnostic accuracy of spirometry and oscillometry will be made by interpretations by a panel of experts to provide a triage diagnosis. The previously developed machine learning AC/DC tool will be used to explore its diagnostic accuracy using oscillometry and spirometry results. This can contribute to standardizing oscillometry in clinical practice.

Objectives	Endpoints			
Primary				
1. To determine whether SADT-c can be used	The predictive value of SADT-c for detecting			
in patients with COPD to detect SAD.	SAD in patients with COPD.			
Secondary				
2. To determine whether the bronze model	Predictive value of SADT-a bronze model for			
SADT-a is predictive for SAD in COPD.	SAD in COPD.			
3. To develop SADT-c.	Agreement between SADT-c results and disease			
	parameters.			
	Content validity and reliability.			
4. To evaluate how SADT-c compares to SADT- a.	Relative predictive value of SADT-a versus SADT-c for SAD in COPD defined as R5–			
a.	$R_{20} > ULN^{1}$.			
5. To determine whether oscillometry and spirometry are equally effective for triage	Agreement between triage diagnoses from oscillometry and spirometry.			
	Relative usability of spirometry and oscillometry.			

Objective:

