3. STUDY DESIGN

The SCOOP-study will be executed in the Netherlands. The study consists of one visit during which all data will be collected. The aim is to include 200 participants in total. Of the 200 patients that will be seen for a visit, approximately 50 participants with previously diagnosed Chronic Obstructive Pulmonary Disease (COPD) and 150 participants without any diagnosis at the time of the visit will be invited. This should result in a total of 200 participants of which 100 are diagnosed with COPD: 50 with a pre-existing diagnosis and 50 newly diagnosed. An overview of the study flow is presented in figure 1.

Participants will visit the site for their usual care, which can be either a follow-up visit for those with an existing COPD diagnosis or a diagnostic visit. In addition to their usual care participants of the study will be asked to complete an oscillometry measurement and a Small Airway Dysfunction Tool for COPD (SADT-c) questionnaire. A panel of international experts will then review the oscillometry and spirometry reports of all 200 participants. Each report will be assessed by 3 to 5 independent pulmonologists in a randomized order. Finally, the triage diagnoses derived from oscillometry and spirometry assessments will be compared. The answers to the SADt-questionnaire items will be compared to the patients' respective SAD status to determine predictive value of SADT-c. Furthermore, ten to fifteen patients with COPD and SAD will be asked to participate in a cognitive interview to assess patient comprehension and necessity of additional questions. In case these are required, 100 COPD patients will be asked to complete the amended questionnaire.

[figure not shown]

Figure 1: Study flow for patients

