5.1 Small Airways Dysfunction Tool (SADT) questionnaire

The SADT questionnaire was developed for patients with asthma and consist of 63 items. SADT items were scored on a 3-point scale (no, yes, unknown)¹⁰. The items reflect specific signs and symptoms which could be suggestive for Small Airways Dysfunction (SAD) or could reflect signs and symptoms that are suggestive for less SAD.

A shorter version of the SADT for asthma with items more tailored to COPD patients will be devised as a part of study. Input from the scientific advisory board (in part the steering committee of the ATLANTIS study¹⁸.) and patient interviews (described in chapter 5.4) will be used. The SADT for COPD (SADT-c) will contain approximately 15 questions.

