6. METHODS

6.1 Study endpoints

6.1.1 Main study endpoint

The primary endpoint is the predictive value of SADT-c for detecting SAD in patients with COPD.

Required variables:

- Diagnosis of Asthma/COPD service
- SAD status defined as R5–R20 > upper limit of normal (ULN)¹
- SADT question results
- Patient characteristics
 - o Age
 - o Sex
 - o Height
 - Body Mass Index (BMI)
 - Age at diagnosis
- Oscillometry and spirometry results

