8.1 Primary study parameter(s)

The primary endpoint is the predictive value of SADT-c for SAD in COPD. The statistical hypothesis for the primary objective is that the predictive value of SADT-c is above the lower limit of the confidence interval of predictive value of SADT-a (AUC 0.74, LR+ 2.3 for the SADT-a bronze model). The hypothesis will be tested at a 2-sided significance level of 0.05.

For the analysis of this primary endpoint, the following population is defined:

- All participants that have a prior or novel COPD (triage) diagnosis, and
- Do not have an asthma, asthma-COPD overlap syndrome, missing or other diagnosis, and
- Have filled in the SADT-c questionnaire.

The presence of SAD will be based on oscillometry results. A resistance difference between 5 and 20 Hz (R5-R20) cutoff of 0.07 kPa x s x L⁻¹ will be used to define the presence of SAD¹⁵.

Analysis will be performed as done earlier for the development of SADT for asthma⁸. In short, to assess the predictive value of SADT-c we first will select the most important SADT items (secondary study parameter). Regression analysis will be used to select SADT items that show a relation with SAD in the expected direction based on the content validity of the items. In a next step the most important SADT items for SAD group will be selected by using logistic regression models. Prediction models using bootstrapping resampling will be used. In addition to the individual SADT items, also patient characteristics, such as age, sex, and height, BMI, will be considered as independent predictors in the model.

Selected key SADT items will be used together with available clinical information to build logistic regression models to predict the SAD group. Three levels of clinical information will be considered resulting in three regression models:

- Bronze: Basic patient characteristics (such as age, sex, age at diagnosis, BMI, or other)
- Silver: Spirometry test results (FEV₁ % predicted)
- Gold: Oscillometry test results (R5-R20 and reactance area (AX)).

For each model the area under the receiver operating characteristic curve (AUC), positive likelihood ratio (LR+) and sensitivity and specificity will be calculated, using a probability cut-off of 0.5 to indicate predicted SAD.

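### Section 8.1 does not say which SADT-c model the primary hypothesis tests, and no model without SADT items is planned to show what the questionnaire adds

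*Protocol*

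**What the plan says.** The hypothesis in Protocol section 8.1 is that "the predictive value of SADT-c is above the lower limit of the confidence interval of predictive value of SADT-a". The figures in brackets there (AUC 0.74, LR+ 2.3) are labelled as those of the SADT-a bronze model. Testing is two-sided at 0.05, and no value is given for the lower limit.

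The same section describes how SADT-c is modelled: "Selected key SADT items will be used together with available clinical information to build logistic regression models to predict the SAD group". It continues: "Three levels of clinical information will be considered resulting in three regression models". Bronze uses basic patient characteristics, silver uses FEV1 % predicted, and gold uses R5-R20 and AX. AUC, LR+, sensitivity and specificity are to be calculated for every model. SAD itself is set in 8.1 by an R5-R20 cutoff of 0.07.

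Elsewhere the label SADT-c is used in more than one way:

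- The Summary speaks of "identifying SAD when combined with key patient and disease characteristics in individuals with COPD (SADT-c", that is, items plus characteristics.
- Section 6.1.1 lists patient characteristics and "Oscillometry and spirometry results" among the variables needed for the primary endpoint.
- Section 5.1 treats it as a questionnaire: "The SADT for COPD (SADT-c) will contain approximately 15 questions".
- Section 3 gives one design sentence: "The answers to the SADt-questionnaire items will be compared to the patients' respective SAD status to determine predictive value of SADT-c".

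The Introduction describes the asthma bronze model as one item (wheezing at rest) plus age, sex, age at diagnosis and BMI. It pairs bronze SADT-a with bronze SADT-c, but as an additional aim and not as the primary hypothesis.

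**The concern.** The primary objective is whether SADT-c can be used to detect SAD in COPD, and section 9.3 expects the analyses to settle its applicability. Two things stand between the planned analysis and that conclusion.

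1. **The tested model is not identified.** One hypothesis, three candidate models and one benchmark leave open which AUC is compared with the limit. The choice matters because each level adds more direct lung-function information.
2. **Nothing described isolates the items.** Every planned SADT-c model contains SADT items and clinical information. The comparison in section 8.2 sets SADT-c models against SADT-a models, which are mixed in the same way. A favourable AUC could therefore come largely from data that section 5 says the service already collects: age, sex, BMI, age of onset and spirometry. Introducing a questionnaire would not follow from such a result.

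**Working it through.** **No plan figure to reproduce.** The AUCs of 0.74, 0.87 and 0.96 in the Introduction are carried over from the asthma study. The protocol derives no AUC of its own, no lower limit and no characteristics-only AUC.

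**Step 1: how much the choice of model matters.** In the protocol's asthma figures, moving from bronze to silver changes AUC by 0.87 − 0.74 = 0.13, and from bronze to gold by 0.96 − 0.74 = 0.22.

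For scale, take the Hanley-McNeil standard error at A = 0.74 with n = 100 and the 74% to 83% SAD prevalence of section 4.4:

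SE² = [A(1−A) + (n1−1)(Q1−A²) + (n0−1)(Q2−A²)] / (n1·n0), with Q1 = A/(2−A) = 0.587 and Q2 = 2A²/(1+A) = 0.629.

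- 74 with SAD, 26 without: SE = 0.052, and 0.74 − 1.96 × SE = 0.639.
- 83 with SAD, 17 without: SE = 0.058, and 0.74 − 1.96 × SE = 0.626.

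If the benchmark were about as precise as this study (an assumption), the limit to beat would be about 0.63 to 0.64. The choice of model moves AUC by more than two of these standard errors.

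**Step 2: gold.** Under 8.1 every patient with SAD has R5-R20 above 0.07 and every patient without SAD does not. If the predictor is the reading that defines the outcome, R5-R20 alone ranks the groups perfectly: AUC = 1.000, confirmed in every simulated trial. The items cannot change this. Under the upper-limit-of-normal definition in section 6.1.1 the limit could differ between patients, so AUC need not be exactly 1, but predictor and outcome would still share the same measurement.

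**Step 3: bronze with items that carry no information.** The simulation used n = 100, 600 trials per setting, four characteristics with an assumed joint true AUC, and 15 pure-noise yes/no items (40% yes). The item most associated with SAD in the expected direction was added. The table shows the share of trials whose apparent AUC reached 0.74.

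| Assumed characteristics-only AUC | SAD 74%: characteristics only | SAD 74%: plus noise item | SAD 83%: characteristics only | SAD 83%: plus noise item |
|---|---|---|---|---|
| 0.50 | <1% | 6% | 5% | 20% |
| 0.60 | 4% | 16% | 12% | 31% |
| 0.65 | 16% | 33% | 27% | 52% |
| 0.70 | 41% | 64% | 49% | 71% |
| 0.74 | 66% | 81% | 72% | 87% |

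Simulation error is at most about 1.96 × √(0.25/600) = 4 percentage points. These AUCs are apparent, so bootstrap correction would lower them. The 0.74 mark is also stricter than the unstated lower limit. The shares are not pass rates of the planned test. They show that the answer turns on an unknown.

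**Step 4: what a useful item would do to bronze.** Suppose 20% without SAD and 40% with SAD answer yes. Alone, the item has AUC 0.5 + (0.40 − 0.20)/2 = 0.60. Added to an independent characteristics score with AUC 0.74, it gives about 0.76. The gain of 0.02 is less than half of one standard error from Step 1 (0.02/0.052 = 0.38; 0.02/0.058 = 0.34). Bronze AUC against a fixed limit therefore cannot show whether the item matters. A paired comparison with the same model minus the item addresses that directly.

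**Step 5: does item selection already protect?** With 15 independent noise items, the chance that at least one reaches one-sided 0.05 in the expected direction is 1 − 0.95^15 = 0.54. In the simulation it was 0.51 to 0.56. Surviving selection does not show a real contribution, and for the same reason an ordinary likelihood-ratio test on the selected items would be too lenient.

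**The case against.** Much of the case on the other side stands. The Summary, the Introduction and section 6.1.1 all present the tool as items used with clinical information, and the SADT-a benchmark is itself a mixed model. Section 8.1 agrees with them. A reader might infer from section 3 that the primary endpoint rests on the questionnaire answers alone and that 8.1 contradicts this. The text does not support that reading: section 3 never says alone and is a short design sentence, and section 5.1 only gives the questionnaire's length.

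The benchmark in the hypothesis is labelled bronze, and nothing proposes setting silver or gold against it, so a bronze-to-bronze reading is natural. That is fair, but the hypothesis does not say so, and 8.1 reports all three models on an equal footing.

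Section 8.1 also requires items to relate to SAD in the expected direction, and 8.2 reports the regression results. Item coefficients adjusted for characteristics would be visible. They say something about contribution, but they come from items picked on the same data (Step 5).

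Finally, section 8 calls itself a summary and leaves detail to a statistical analysis plan. A comparison with and without items could appear there, so its absence alone would be a weak point. What the hypothesis tests, however, is stated in the protocol, and it is stated incompletely.

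**Conclusion.** The concern holds in a limited form. The primary hypothesis does not identify the SADT-c model it tests, and the plan as described has no model without SADT items. Meeting the hypothesis therefore need not reflect the questionnaire.

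For gold this is certain under the 0.07 cutoff, given that the same R5-R20 reading serves as predictor and outcome. For silver and bronze it is a possibility. Its likelihood depends on a characteristics-only AUC that the protocol does not give: the bronze shares in Step 3 run from 6% to 87% across assumed values of 0.50 to 0.74.

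A reader might go further and conclude that SADT-c would pass almost automatically, or that a pass would owe nothing to the items. The documents do not support that. It requires assuming that the characteristics carry the whole asthma bronze AUC, that the items are null, and a particular lower limit. Nor is combining items with characteristics a flaw.

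**What to change.** In section 8.1, and in the statistical analysis plan before database lock:

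1. State that the primary hypothesis concerns the bronze SADT-c model against the bronze SADT-a benchmark. Make silver and gold secondary.
2. For bronze and silver, also fit the same model without SADT items. Report the difference in optimism-corrected AUC with a confidence interval, from a bootstrap that repeats the item selection in each resample. Do not use an ordinary likelihood-ratio test on the selected items. The comparison is uninformative for gold while R5-R20 defines SAD.
3. Interpret the primary result alongside this difference. Attribute detection of SAD to the questionnaire items only if they add to the characteristics-only model. Otherwise, confine the claim to the combined model.

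The cost is wording plus two extra models and a somewhat heavier bootstrap on data already collected. A claim about the questionnaire itself becomes harder to support. With only 17 to 26 patients without SAD expected among 100, the interval for the difference may be wide, and an inconclusive difference should not be read as proof that the items are useless.

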6.1.2 Secondary study endpoints

The secondary endpoints are:

- 1. Predictive value of SADT-a bronze model for SAD in COPD.
- 2. Agreement between SADT-c results and disease parameters.
- 3. Content validity and reliability.
- 4. Relative predictive value of SADT-a versus SADT-c for SAD in COPD defined as R5– R20 > ULN¹
- 5. Agreement between triage diagnoses from oscillometry and spirometry.
- 6. Relative usability of spirometry and oscillometry.

Required variables:

- 1.
- Triage diagnosis of Asthma/COPD service
- SAD status based on oscillometry test (R5-R20)
- SADT question 8
- Patient characteristics (bronze model)
 - o Age
 - o Sex
 - o Height
 - o Body Mass Index (BMI)
 - Age at diagnosis
- 2.
- Triage diagnosis by Asthma/COPD service
- SAD status based on oscillometry test (R5-R20)
- Lung function results

- Asthma/COPD service collected questionnaires and patient characteristics (as described in chapter 5)
- SADT-c variables
- Patient characteristics bronze model
- 3.
- Cognitive interviews
- SADT-c results
- 4.
- Predictive value SADT-a different models
- Predictive value SADT-c different models
- 5.
- Panel expert diagnoses (spirometry)
- Panel expert diagnoses (oscillometry)
- Patient characteristics
- Difficulty to diagnose (scale)
- 6.
- Operator opinion
- Expert interpreter opinion
- Duration of measurement
- Patient burden

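### The gold model predicts SAD from R5-R20, the measurement that defines SAD, so its accuracy is fixed by definition and says nothing about SADT-c

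*Protocol*

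**What the plan says.** Protocol section 8.1 fixes the outcome: "resistance difference between 5 and 20 Hz (R5-R20) cutoff of 0.07 kPa x s x L⁻¹ will be used to define the presence" of SAD. The same section then says: "Selected key SADT items will be used together with available clinical information to build logistic regression models to predict the SAD group". Three tiers follow. Bronze uses basic patient characteristics, silver uses FEV1 % predicted, and the third is "Gold: Oscillometry test results (R5-R20 and reactance area (AX". AUC, LR+, sensitivity and specificity are reported for every tier, "using a probability cut-off of 0.5 to indicate predicted SAD".

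Section 6.1.1 states the outcome differently: "SAD status defined as R5–R20 > upper limit of normal (ULN". Secondary endpoint 4 in section 6.1.2, the interview selection in section 6.2 and the Summary also use the ULN.

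The primary hypothesis in section 8.1 sets SADT-c against the lower confidence limit for SADT-a and quotes only the bronze figures (AUC 0.74, LR+ 2.3). It continues: "The hypothesis will be tested at a 2-sided significance level of 0.05". It does not name the SADT-c tier to be tested. For secondary endpoint 4, section 6.1.2 lists "Predictive value SADT-c different models" and the SADT-a counterpart, and section 8.2 compares the various models of the two tools. Section 1 gives the asthma gold model as AUC 0.96 and LR+ 12.8.

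**The concern.** A prediction model is informative only if the outcome is established independently of the predictors. Here the reference standard is a threshold on R5-R20, and R5-R20 is entered as a predictor. The gold model can recover the outcome without using a single questionnaire item, so its accuracy describes the definition of SAD and not the tool.

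Two things are at stake. First, a tier reported under the primary parameter would show perfect or near-perfect accuracy that a reader could credit to SADT-c. Second, the gold level of secondary endpoint 4 cannot separate the two tools. Section 8.2 also makes the adding of new items depend on SADT-c performing significantly worse than SADT-a, without naming a tier. If both tools are fitted to the COPD patients at gold level, that shortfall could hardly appear.

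**Working it through.** The protocol gives no expected accuracy for the gold model in COPD, so there is no stated figure to reproduce. The check asks what the gold model must return if the SADT items carry no information.

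**Inputs from the protocol.** 100 COPD patients and SAD prevalence 74% to 83% (section 4.4); cutoff 0.07, gold predictors R5-R20 and AX, probability cutoff 0.5 (section 8.1); alternative outcome R5-R20 > ULN (section 6.1.1).

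**Step 1: fixed cutoff, same measurement.** This step needs no assumption about distributions.

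- 100 × 0.74 = 74 SAD and 26 non-SAD; 100 × 0.83 = 83 SAD and 17 non-SAD.
- AUC is the share of SAD/non-SAD pairs in which the SAD patient has the higher score. Every SAD patient lies on the upper side of 0.07 and every non-SAD patient on the lower side, so all 74 × 26 = 1,924 pairs (or 83 × 17 = 1,411) are correctly ordered. AUC = 1.00.
- Sensitivity = 74/74 and specificity = 26/26 (or 83/83 and 17/17), both 100%. LR+ = sensitivity / (1 − specificity) = 1/0, undefined.
- Take the linear predictor β(R5-R20 − c), with c between the highest non-SAD and the lowest SAD value. As β grows, every fitted probability tends to its observed outcome and the log-likelihood rises towards 0 without reaching it. No finite maximum-likelihood estimate exists. Adding items, AX or patient characteristics does not help, because setting their coefficients to zero leaves the separation in place. The item coefficients cannot be interpreted.

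**Step 2: simulation with noise items.** n = 100, 400 replicates. Assumed: log-normal R5-R20 with log-SD 0.6, AX correlated 0.8 with log R5-R20, and two SADT items that are pure noise. A negligible ridge penalty was used so that separated data still return a fit. For the ULN definition the threshold varied between patients around 0.07 on the log scale. A further case took predictor and outcome from two different measurements, such as pre- and post-salbutamol.

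| Outcome definition | Gold AUC, prevalence 74% | Gold AUC, prevalence 83% |
|---|---|---|
| Fixed 0.07, same measurement | 1.000 | 1.000 |
| ULN, log-SD 0.1 | 0.995 | 0.996 |
| ULN, log-SD 0.2 | 0.975 | 0.982 |
| ULN, log-SD 0.3 | 0.947 | 0.957 |
| Two measurements, correlation 0.95 | 0.978 | 0.983 |
| Two measurements, correlation 0.90 | 0.953 | 0.959 |
| Two measurements, correlation 0.80 | 0.901 | 0.916 |

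An unpenalised logistic fit under the fixed cutoff did not converge, as step 1 predicts. Coefficients from such a fit are not estimates and are not quoted.

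**Step 3: reading the ULN rows.** The protocol does not give the ULN formula, so the spread is an assumption and is shown as a range. Age, sex and height are among the candidate predictors. If the ULN is calculated from them and the model keeps them, accuracy would move further towards 1. This was not computed.

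**Step 4: which tiers are affected.** Bronze uses patient characteristics and silver uses spirometry. Neither contains an oscillometry value, so steps 1 and 2 do not apply to them.

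**The case against.** The strongest reply is that the primary conclusion does not rest on the gold model. The only benchmark figures in the hypothesis are bronze, section 1 describes a bronze-to-bronze comparison, and secondary objective 2 is bronze only. This stands. A reader might infer that the circularity invalidates the primary endpoint; the protocol does not support that. What remains is that section 8.1 lists gold among the primary-parameter models and does not say which SADT-c tier is tested.

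A reader might also infer that a gold AUC near 1 would be presented as SADT-c beating the asthma gold model's 0.96. Secondary endpoint 4 concerns SAD in COPD for both tools, and section 1 gives 0.96 only as background. If both tools are fitted in these patients, both contain R5-R20 and both approach 1. The result is an empty tie, not a false win.

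It can be said that the ULN definition avoids the problem. It removes the certainty of complete separation, and that qualification stands, but the outcome is still a threshold on R5-R20. Likewise, outcome and predictor might come from different measurements at diagnostic visits. The protocol does not say so, and the result would then reflect the repeatability of R5-R20.

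Section 8.1 follows the asthma analysis. How SAD was defined there is not in the document. An asthma AUC of 0.96 suggests that the outcome was not a plain cutoff on the same R5-R20 value, but this is an inference and the conclusion does not need it.

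Deferral to the statistical analysis plan does not answer the point, because the protocol itself fixes both the outcome and the gold predictors. AX is a lesser matter: it comes from the same test but is not determined by R5-R20, so it calls for a caveat.

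**Conclusion.** The concern holds for the gold tier of section 8.1 and the gold-level part of secondary endpoint 4 in section 8.2. There the result is uninformative about SADT-c.

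Under the 0.07 rule with one measurement, perfect accuracy and complete separation follow from the text alone. Under the ULN rule, near-perfect accuracy with useless items (AUC about 0.95 to 0.995) rests on the assumed ULN log-SDs of 0.3 to 0.1 and the other simulation settings, and complete separation is possible but not certain. Bronze and silver are not circular, and the bronze benchmark of the primary hypothesis is untouched.

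**What to change.** 1. In section 8.1, remove R5-R20 from the predictors of any SADT-c model for SAD defined by R5-R20.
2. Exclude the gold level from the primary conclusion (8.1) and from the SADT-a versus SADT-c comparison (8.2).
3. If an oscillometry tier is kept, fit it with AX only, label AX as coming from the same test as the reference standard, and report it descriptively.
4. State in section 8.1 that the primary hypothesis is tested on the bronze SADT-c model.
5. Reconcile the two definitions of SAD, 0.07 in section 8.1 and ULN in sections 6.1.1, 6.1.2 and 6.2, so that one outcome applies throughout.

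The cost is wording only: one tier is dropped or relabelled, and no new data are needed. Section 8 says the statistical analysis plan will be finalised before database lock, so the change can be made in time.
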